### **Definitions used for the indicators of objective 2**

Positive impact modification is defined as a change in the algorithm expected to increase the clinical cure rate and/or decrease resources needed\* and/or to have another positive clinical or health system related impact.

\* Resources needed include but are not limited to medicines prescribed, diagnostic tests ordered by HWs, or time spent to perform a consultation.

## 7.3 Indicators for Objective 3: Enhance M&E and supportive supervision

- Number of M&E indicators based on individual data that can be visualized through the medAL-monitor/medAL-outbreak dashboard
- Number of supervision and mentorship visits to HFs facilitated by the medAL-monitor tool
- Number of HWs reporting having used the medAL-monitor tool for self-auditing their clinical practices
- Number of HWs and members of DHMT reporting a positive experience with the medAL-monitor/medAL-outbreak tool

[figure not shown]
## 7.4 Indicators for Objective 4: Create a supportive environment for the use of clinical algorithms and supporting tools

- Number of sick children attending primary care facilities managed by HWs using the electronic ePOCT+ tool
- % of HWs able to assess key clinical signs
- Frequency of use of the medAL-monitor/medAL-outbreak tool by district team members
- Perception by HWs of the ePOCT+ tool and intervention and the number of improvements they propose for the tool or intervention
- Perception by caregivers and community members of the intervention and the number of improvements they propose
- Perception by district team members of the medAL-monitor/medAL-outbreak tool and the number of improvements they propose for the tool
- Number of medical experts able to modify a clinical algorithm using medAL-creator
- Number of computer scientists able to maintain the software and the IT infrastructure for clinical algorithms
- Number of data scientists able to analyze clinical data using ML
- Perception of the current and future utility of ML to improve health care amongst clinical experts (deciding on algorithm changes) and health authorities
- Patient and provider expenditures related to care of acutely ill children included in the study
- Carbon footprint of the intervention or carbon-saving due to the intervention

## 8 STUDY PROCEDURES

A flowchart summarizing the study procedures is presented in **Figure 10**.

**Figure 10:** Flowchart of health facilities and patients included in Phases 1 and 2

## 8.1 Objective 1: Improve the integrated management of sick children

### 8.1.1 Recruitment, screening and informed consent procedure

As the intervention is implemented at the facility level, approvals from relevant authorities will be sought before engaging with persons in charge of HF and HWs. Sensitization meeting will be organized in the sectors, cells and villages within the catchment areas of enrolled HF. District and HF consent will be obtained for the intervention. HF will be informed which group they have been selected for within the parallel cluster study design and when they will receive the intervention. HF in groups 2, 4, and 6 will also be made aware that they will be asked to use study tablets and enroll patients to contribute baseline/control data for four months prior to receiving the intervention. Individual consent from caregivers (and assent from older children) will be sought for electronic recording of data and follow-up by phone call or SMS or home visit. Upon the start of the study, information will be provided in the waiting areas of facilities.

All patients in the HF will be systematically screened for eligibility. All children aged 1 day to 14 years (inclusive) presenting for an acute problem to a HF that is part of the study will be asked if they wish to participate in the study by the person usually doing registration of patients or another appropriate person trained in ascertaining consent (using the registration module in the tablet). The consent process will be integrated into the routine workflow at the HF to the extent possible. Caregivers will be asked consent for registration, electronic data recording for this and subsequent visits to the HF, and follow-up by phone or SMS or home visit for their child. They will be informed that not providing consent will not affect the medical management of their child and the child can still benefit from being managed by the ePOCT+ tool and that their data will not be used for research purposes. All caregivers will be provided a paper-based participant information sheet and consent form providing sufficient information to make an informed decision about their participation in the study. If the clinical condition of the child requires immediate treatment, this will supersede the written consent process, which will be conducted once the child is stabilized. Consent that remains at the HF will be documented electronically, either by obtaining the signature directly on the tablet, or by storing a photo of the signed paper consent form as part of the digital registration of the child. Because of the longitudinal nature of the study, a full consent process will be conducted two times throughout the study: at first visit in Phase 1 and at first visit in Phase 2. Otherwise, consent will be ascertained using a simple check-box within the ePOCT+ registration/check-in module during each visit.

A separate consent process will be used for the participants of the mixed-methods operational research studies. For example, as part of the cross-sectional quality of care surveys, trained research clinical observers will ask HWs present on the day of data collection for permission to observe a series of consultations. They will then ask the HW to request oral permission from their patient and to sign a consent form indicating their own and the patient's consent to have an observer in the room. The caregiver will also give consent to be subsequently interviewed by a different research assistant upon the completion of their consultation. Similarly, the participants of qualitative interviews or FGDs, or quantitative surveys will be recruited and asked for their consent to participate. The Informed Consent Forms associated with the study can be found in **Appendix C**.

### 8.1.2 Management of sick children during the initial consultation

In HF with dedicated staff for triaging patients, sick children will first be assessed by this person using the triage module of ePOCT+ in the tablet. If the child requires urgent treatment, the triaging person will immediately inform the attending HW(s), so that he/she can give priority to that child over others waiting to be seen. If not, the child will queue normally and be attended by the next available HW. As part of triage, the vital signs will be measured (temperature, respiratory rate, weight and MUAC) as well as, if the child fulfills certain clinical criteria, oxygen saturation and heart rate using the pulse oximeter. If there are no dedicated triage staff, the triage module will be de-activated and vital signs will be measured during the consultation.

The attending HW will either manage the child using the ePOCT+ algorithm or as per routine (depending on the stage of implementation in that particular HF). HWs are ultimately responsible for the clinical management of all patients and may override the recommendations of the algorithm and provide additional or withhold treatment according to their own clinical judgment. All concomitant diagnostic interventions and treatments will thus be left at the discretion of the provider but recorded in the ePOCT+ tool. While being managed with ePOCT+, if the child needs to go to another room for laboratory investigations (rapid tests or other), the HW will be able to suspend the data recording in the tablet and open a parallel session to attend another child in the meantime. When the child returns with the test results, the HW will resume the ePOCT+ algorithm and data recording of that child and continue the consultation normally.

At the end of the consultation, the HW (in both control and intervention facilities) will be asked to enter the final decision on referral, tests performed, final diagnoses and treatments prescribed (see Section 8.1.6 on outcomes measures). After the consultation, this information will be synced to the server as soon as there is internet connectivity.

It is assumed that usual diagnostic tests and treatments will be provided through the routine health care system. The majority of the Rwandan population, including children, are covered by a health insurance policy, which partially covers the cost of their outpatient visit (consultation cost is approximately 200 Rwandan francs but can vary depending on the socioeconomic category of the household). When not available at the HF, patients purchase their medications from private pharmacies that charge out-of-pocket. To allow testing of the intervention under conditions as close as possible to those expected for future implementation, we will not provide routine diagnostics or medications in either the control or the intervention facilities. However, we will ensure that immediate life-saving treatments are available and will support the facility staff in managing stocks through routine mechanisms. POC tests that would normally be unavailable in the PHC setting (i.e. CRP test), or available in lesser quantity than is required for the study (e.g. Hb test) will be provided to the HFs and the patients at no additional cost.

### 8.1.3 Re-attendance visits in case of persisting or worsening of symptoms

At initial consultation, the advice to caregivers on when to bring the child back to the HF is left at the discretion of the HW. During Phases 1 and 2, HWs will be guided by the ePOCT+ tool, which recommends conditional follow-up based on WHO and national guidelines. At re-attendance visits, whether scheduled or unscheduled, children will be managed in the same way as all other children in that particular facility at that time (ePOCT+ or routine care). If the child comes back to the same HF that uses ePOCT+ as for the initial consultation, the HW will have access to the electronic data of that initial consultation that is saved in the HF tablets. If the child goes to a different HF participating in the study, the HW will not have access to that data. Investigators will however be able to link data collected at different facilities (as long as they are part of the study) for the same child through the unique identification number provided to caregivers. If the child goes to a HF not participating in the study, no data will be available for that consultation. The ePOCT+ registration module, used at all participating facilities, will inquire about the type of visit (initial/scheduled re-attendance/unscheduled re-attendance) and the main reason for that visit.

### 8.1.4 Training of health workers

Following the study design, training of HWs will be rolled out in a sequential manner. Each implementation block includes facilities that will receive the intervention right away (e.g. group 1) and facilities that will start with a 4-month control period (e.g. group 2) that require different training approaches.

Before the start of the control period (applicable to groups 2, 4 and 6): All skilled HWs who are engaged in triage, assessment, and clinical management of sick children will receive training in study-

related procedures, including consent for electronic recording of data and documentation of the final decision on referral, tests performed, final diagnoses and treatments using the tablet. Additionally, the research team will ensure that the standard paper guidelines (IMCI and Rwandan national treatment guidelines) are available in all HFs and HWs will be reminded that these guidelines should be followed during patient management.

Before the start of Phase 1 (applicable to all groups except group 6): HWs will receive training on how to use the ePOCT+ application on the tablet, using clinical case studies, as well as job aids for conducting and interpreting the results of POC tests which are not currently part of standard care at PHC level but are included in the algorithm (e.g. pulse oximetry and CRP rapid test). HWs will also be trained on the epidemiology of diseases in Rwanda, the most important pediatric diseases and their clinical predictors, and the importance of rational antibiotic and antimalarial use. They will also be able to review the content of the ePOCT+ algorithm and practice key clinical skills via the use of the e-learning tool. Additionally, training will be provided on the use of the medAL-monitor/medAL-outbreak tool (see Section 8.1.5).

During the month following this centralized training, HWs in control facilities will benefit from one and in intervention facilities from two visits from the implementation team for in-service face-to-face training during which trainers will accompany them in some of their consultations with real patients and help them optimize the way they use ePOCT+. Trainers will also support reorganization of workflows in the HF if necessary.

Before the start of Phase 2 (applicable to all groups): all HWs will be gathered for a brief refresher training (except group 6 will receive the full training) and to prepare them for Phase 2, where they will occasionally receive notifications that a new version of the algorithm has been released on their tablet and what that means for their management of the patients. During this refresher training, key clinical skills of the HWs will be re-assessed to evaluate whether the use of ePOCT+ and the e-learning modules has improved their clinical competencies, with anticipated differences across implementation groups associated with varying length of use of the application.

During both Phases 1 and 2, new personnel at study facilities will be trained through a dedicated module on the tablet and by their peers. This module will be available to all HWs using ePOCT+ so that they can refresh their knowledge at any time.

### 8.1.5 Supervision of health workers by the DHMT

In Phases 1 and 2, the DHMT will be provided the medALmonitor/medAL-outbreak tool with dashboards enabling them to monitor indicators (see **Table 3**) related to pediatric consultations taking place in the HFs enrolled in the study. Data on the child's or the HW's identification will not be provided, only the name of the health facility will be available. Based on these indicators, the supervision team will be able to better organize on-site visits to HFs, prioritizing the lowest performing ones, knowing in advance what areas of improvement to concentrate on. The persons in charge of HFs, as well as individual HWs, will also have access to these indicators (fully anonymized except for their own data) to allow them to do self-auditing at HF level so that they are aware of their own performance in advance of receiving a DHMT supervision visit. The aim of the medAL-monitor/medAL-outbreak tool is to stimulate HWs' motivation and self-leadership to improve their skills and competencies, while enabling the supervision team to help them resolve remaining problems (Bessat et al. 2019).

### 8.1.6 Measurement of primary and secondary outcomes

*Data captured on the tablet used by health workers during the consultation*

Prior to the beginning of the control period (applicable to groups 2, 4 and 6), tablets will be provided to HWs that will contain only the patient registration and abbreviated end-of-consultation modules. Prior to Phase 1 (applicable to all facilities), the ePOCT+ application will be released onto the tablets that will contain the same patient registration module followed by the ePOCT+ algorithm that will guide them throughout the consultation process (see **Appendix A**).

To determine the percentage of children prescribed an antibiotic or an antimalarial, as well as to know the final decision on referral and final diagnoses retained by HWs, five questions will appear on the screen at the end of the consultation process, i.e. once the clinician has gone through the entire algorithm in the intervention facilities or just after the patient registration module in the control facilities. HWs will be asked to document (1) the final decision regarding the need for referral, (2) tests performed and the results, (3) date of follow-up if needed, (4) final diagnoses and (5) final treatments prescribed. For each medicine prescribed, the dosage and duration of the treatment will also be recorded (see **Appendix A**).

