## 9 STATISTICAL METHODS

### 9.1 Sample size calculations

For the parallel cluster study in Phase 1, the primary analysis will evaluate whether the use of ePOCT+ for case management of sick children in PHC facilities results in decreased antibiotic prescriptions (superiority analysis) at the initial consultation. Superiority in antibiotic prescription is defined as a relative decrease of  $\geq 25\%$  in the proportion of children prescribed an antibiotic. We estimated a cluster size of 660 patients (monthly utilization of 220 – accounting for up to 30% non-adherence from 315 – over 3 months) and an intraclass correlation coefficient of 0.025. Non-adherence here is defined as HWs not using the application for all eligible patients that come to the HF for various reasons. To have 80% power to detect a 25% reduction in antibiotic prescription (e.g. from 35% to 26%), for a one-sided hypothesis test at alpha of 0.05, we would require a minimum of 11 clusters per arm. With 16 clusters (or HF) over 3 months, we expect a total of 10,500 participants per arm, this sample size is

sufficient to test for non-inferiority in the secondary outcome (clinical cure at day 7) between the control and intervention groups.

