## 9.2 Statistical analysis for the primary outcome measure in the parallel cluster study

Analyses will follow CONSORT guidelines (Schulz et al. 2010, Piaggio et al. 2012). A flowchart will describe the inclusion and follow-up of participants by study arm and by implementation block. Baseline characteristics and outcomes will be described by study arm and by implementation block using summary statistics such as median and interquartile range or number and percentage.

We will test for significant difference in the primary outcome of antibiotic prescription between study arms by comparing proportions and their 95% confidence intervals (CI). Primary analysis of superiority will be performed according to the intention-to-treat (ITT) principle (Committee for Proprietary Medicinal Products, 2001), with sensitivity analyses exploring differences between ITT, per-protocol and complete cases analysis approaches. The results will be stratified by sex, age group (young infants ages 1 to 59 days, children aged 2 months to 5 years, and children aged 5 to 14 years), and select clinical variables (respiratory symptoms, fever without clinical source, gastrointestinal complaints, skin problems, ear and throat problems, anemia, and malnutrition).

We will also use multi-level logistic regression with HF, patient ID, and time included as random effects (Kahan et al. 2012) to explore the effect of demographic and clinical variables on the outcome of interest. Effect modification by sex, age group, and the same clinical variables will be assessed by incorporating an interaction between arm and the respective variable, acknowledging that power will be low.

Primary analysis will be performed on initial consultations only (i.e. first visit for a particular illness episode), allowing multiple observations per patient over the course of Phase 1, but only one observation per illness. We will apply a 14-day period from the initial visit, during which no second initial visit will be possible and all subsequent visits will be marked as re-attendance by default. In the secondary sub-analyses, re-attendance visits between day 0 and day 7 will be considered, as well as longitudinal analyses of the complete visit history per patient. Further details on the primary and secondary analyses will be provided in the statistical analysis plan.

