2.1 Outcome definitions

2.1.1 Primary outcome

Percentage of children prescribed an antibiotic at initial consultation in the intervention group (ePOCT+) as compared to the control group (routine care)

Outcome measure: Prescription of oral or parenteral antibiotic at initial consultation, as reported by the HW.

Timing and method of measurement: Documented by the HW at the end of the initial consultation where the subject was enrolled (day 0).

Analysis type: Superiority

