Since the intervention takes place at the health provider level and their practices are influenced by the context of the health facility they are working in, randomization at health facility level rather than at HCW level or at individual patient level was chosen. The randomization of clusters (i.e. health facilities) will be performed on a 1:1 ratio. Thus, ePOCT+ will be provided to health workers (HWs) of 16 of the 32 selected primary health care facilities (intervention arm) in Rusizi and Nyamasheke districts, while the other 16 health facilities (HFs) will serve as controls (control arm). Sick children aged 1 day to 14 years (inclusive) will be managed in accordance with the study arm to which the HF they attend has been assigned. The comparator for Phase 1 will be routine care as currently implemented in Rwanda supplemented with equivalent clinical training given to the intervention arm. To assess the primary and secondary outcomes, final decision on referral, laboratory test results, diagnoses and treatments at initial consultation will be recorded by HCWs electronically in both arms (in the intervention arm integrated into the CDSA; in the control arm via a simple eCRF without any decision support); children will also be followed-up by a phone call or home visit to their caregiver at day 7 (range 6-14) to determine their clinical status. The study is considered as pragmatic since there are no major exclusion criteria to the population of interest, and the setting and organization of the health facilities remains mostly the same. The trial design is summarized below. Furthermore, in line with the pragmatic nature of the study, the design is adaptive, in that changes in the implementation across the three parallel cluster studies may be made based on monitoring data and feedback from the health facilities. These implementation changes (excluding significant adaptations to algorithm content) will be thoroughly documented and accounted for in comparisons across the three cluster studies.

PHASE 1

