4.2 Analysis population definitions

Intention-to-treat population: This population includes all patients enrolled in the study, regardless of whether the HW used ePOCT+ (intervention arm), or entered the final treatment data in the eCRF (both arms).

Per-protocol population: This population only includes patients enrolled in the study for whom the clinician confirmed the final treatment (or absence of treatment) / referral status within the ePOCT+ tool (intervention arm) or in the eCRF (control arm).

Complete case set: All enrolled subjects (intervention or control) for whom day 7 clinical cure data was collected (i.e. excluding lost to follow-up patients).

Complete consultation set: All enrolled subjects (intervention or control) for whom at least information on treatments were collected at day 0.

5. Study population

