6.1 Analysis methods

Analyses will follow CONSORT guidelines (Campbell, Piaggio, Elbourne, & Altman, 2012; Piaggio et al., 2012; Schulz, Altman, & Moher, 2010; Zwarenstein et al., 2008). Outcomes will be described by arm using summary statistics. Baseline characteristics will be compared by study arm and by cluster study to ensure that the pragmatic allocation of health facilities and sequential rollout of the study did not introduce significant bias. Baseline characteristics which will differ between treatment arms within and over all clusters will be described using summary statistics.

Since the documentation of final treatment in both arms is part of the per protocol definition, only the PP population can be used for primary outcome analysis. The primary outcome will be evaluated using a random effects logistic regression model with the binary outcome variable of antibiotic prescription, with study arm and covariates at patient-level (e.g. age, sex) as fixed effects, and cluster (health facility) and patient included as random effects. Binary secondary outcomes will be evaluated in the same way. All estimates will be reported as odds ratios (ORs) with two-sided 95% confidence intervals (CI). The study will be deemed a success if antibiotic prescription at the initial consultation is 25% less in the ePOCT+ arm compared to the control arm, although we expect a greater reduction based on limited pilot data.

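### Treatment entry comes at the end of ePOCT+ in one arm and straight after registration in the other, so missing primary outcomes can depend on use of the intervention

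*Protocol*

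**What the plan says.** The primary outcome is an antibiotic prescription reported by the health worker. SAP 2.1.1 gives its timing: "Documented by the HW at the end of the initial consultation where the subject was enrolled (day 0".

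Protocol 8.1.6 describes five closing questions, one of them on final treatments. They appear "once the clinician has gone through the entire algorithm in the intervention facilities or just after the patient registration module in the control facilities". SAP 3.1 describes the same split in tools: "in the intervention arm integrated into the CDSA; in the control arm via a simple eCRF without any decision support". SAP 6.2 refers to ePOCT+ itself as the intervention arm's eCRF, so no separate intervention form is described.

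On analysis sets, SAP 4.2 defines the per-protocol population: "This population only includes patients enrolled in the study for whom the clinician confirmed the final treatment", or its absence, within the ePOCT+ tool in the intervention arm and in the eCRF in control. The intention-to-treat set takes all enrolled children "regardless of whether the HW used ePOCT+ (intervention arm), or entered the final treatment data in the eCRF (both arms". SAP 6.1 then states that "only the PP population can be used for primary outcome analysis". Protocol 9.2 says something different: "Primary analysis of superiority will be performed according to the intention-to-treat (ITT) principle".

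SAP 4.1 measures adherence as the share of enrolled children with a final treatment entered, and describes it by arm.

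**The concern.** In control facilities the outcome screen is one step from registration. In intervention facilities it follows the whole algorithm, in a consultation that protocol 3.1 expects to average 15 minutes. Protocol 11.2 itself lists reluctance to use the tool as a risk. A health worker may register a child, start ePOCT+, stop and carry on as in routine care. For that child the documents describe no place to enter what was prescribed.

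Whether the primary outcome is observed can then depend on whether the intervention was carried through. The comparison becomes completed ePOCT+ consultations against recorded control consultations. The pragmatic question is what happens to prescribing among enrolled children when a facility is given ePOCT+, and that may have a different answer.

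The choice of analysis set cannot repair this. A child with no treatment entry has no outcome under intention to treat either. The missing-data discussion in SAP 6.1 concerns loss to follow-up at day 7, not a missing antibiotic entry. SAP 5.4 adds that clinical signs and comorbidities are not collected systematically, which limits any model-based correction.

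**Working it through.** **1. The plan's own sample size.** Inputs from SAP 3.3: 35% against 26%, two-sided alpha 0.05, 80% power, cluster size 660, ICC 0.025.

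- Individual n per arm = [1.96·√(2·0.305·0.695) + 0.8416·√(0.35·0.65 + 0.26·0.74)]² / 0.09² = 410 after rounding up.
- Design effect = 1 + (660 − 1)·0.025 = 17.475.
- Clusters per arm = 410·17.475/660 = 10.86, so 11, as stated.
- 16·660 = 10,560, in line with the stated 10,500 per arm.

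**2. Power is hardly affected.** Suppose 20% of records are lost in the intervention arm only, with 16 clusters per arm.

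- Intervention cluster size = 528, with design effect 1 + 527·0.025 = 14.175.
- Variance of the difference = 0.2275·17.475/10,560 + 0.1924·14.175/8,448 = 0.000699.
- Power = Φ(0.09/√0.000699 − 1.96) = 92.6%, against 92.7% with no loss.

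The issue is bias, which more recruitment would not remove.

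**3. Sensitivity of the estimate.** Let *f* be the share of enrolled intervention consultations with no treatment recorded, and *a* the antibiotic rate among them. Both are assumed, because the documents give neither. Control is taken as 35% throughout, which means that control has no unrecorded consultations or that they are also treated at 35%.

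- Intervention rate over all enrolled = (1 − *f*)·0.26 + *f*·*a*
- Relative reduction = 1 − (that rate)/0.35
- With *f* = 0: 1 − 0.26/0.35 = 25.7%

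| *f* | Rate, *a* = 35% | Reduction | Rate, *a* = 26% | Reduction |
|---|---|---|---|---|
| 5% | 0.95·0.26 + 0.05·0.35 = 26.45% | 24.4% | 26% | 25.7% |
| 10% | 0.90·0.26 + 0.10·0.35 = 26.9% | 23.1% | 26% | 25.7% |
| 20% | 0.80·0.26 + 0.20·0.35 = 27.8% | 20.6% | 26% | 25.7% |

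If *a* lies below 26%, the recorded figure understates the reduction.

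**4. Dependence on the starting point.** The planning rates sit just above the 25% criterion in SAP 6.1, so any dilution quickly falls below it. The crossing point at *a* = 35% is (0.2625 − 0.26)/(0.35 − 0.26) = 2.8% unrecorded. A larger effect leaves more room. With a recorded intervention rate of 20%, the recorded reduction is 1 − 0.20/0.35 = 42.9%. With *f* = 20% and *a* = 35%, the rate is 0.80·0.20 + 0.20·0.35 = 23.0% and the reduction is 34.3%, still above the criterion.

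**The case against.** The strongest reply is that protocol 8.1.6 says when the questions appear, not that they are locked until every step is done. Protocol 3.1 lets clinicians move freely through the algorithm. Protocol 8.1.2 allows a session to be suspended and resumed, and allows recommendations to be overridden with treatment still recorded. SAP 6.2 tracks the share of intervention children with basic measurements documented and the share of cases managed with ePOCT+. Both suggest that incomplete or unguided records may exist. SAP 4.2 mentions eCRF entry for both arms, which could mean that a route is available. The screen logic is in Appendix A, which is not reproduced. A reader might infer that no route exists at all, but the documents support only that none is described.

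A reader might also infer that outcomes go missing in the intervention arm alone. Control workers can leave treatment blank too, and SAP 4.1 reports entry for both arms. What stands is a heavier hurdle, tied to use of the intervention, in one arm.

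A third tempting reading takes the planned 30% as the abandonment rate. Protocol 9.1 rules that out: "Non-adherence here is defined as HWs not using the application for all eligible patients". That mainly concerns eligible attendees for whom the application is not used, and the SAP figure also covers loss to follow-up. No rate of stopping after registration is given.

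Monitoring (protocol 11.3), completeness checks (protocol 10.4) and by-arm adherence (SAP 4.1) would help to detect the problem. They do not recover the lost outcomes.

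**Conclusion.** The concern holds as a risk built into data capture. Protocol 8.1.6 states the asymmetry outright. Together with SAP 3.1, 4.2 and 6.1 it means that an intervention consultation not carried to the end screen drops out of the primary analysis, unless an exit exists that the documents do not describe.

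The direction and size of the bias cannot be derived from the documents. The 24.4%, 23.1% and 20.6% are illustrations. They rest on recorded rates of 35% and 26%, an assumed 5%, 10% or 20% unrecorded, treatment of those children at the control rate, and no distortion in control. They should not be read as the true reduction, or as showing that the trial would miss its 25% criterion. There is no bias if unrecorded children are treated at 26%, and SAP 6.1 expects an effect larger than 25%.

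The disagreement between protocol 9.2 and SAP 6.1 on the primary analysis set is a separate inconsistency. Resolving it would not recover the missing entries.

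**What to change.** - **Protocol 8.1.6:** allow the abbreviated end-of-consultation module to be opened at any time after registration on intervention tablets. If this is already possible, say so. Add one field for ePOCT+ status: completed, stopped part-way, or not used.
- **Both arms:** require a treatment entry, or confirmation that none was given, before a case can be closed.
- **SAP 4.2 and 6.1:** count these records in the intervention arm for the primary outcome, and make clear what eCRF entry in both arms means.
- **Reporting:** give treatment-entry completion by arm beside the primary result, with the intervention arm split by the new field. The same field can supply the uptake measure in SAP 6.2.

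The cost is a small change to the tablet application plus the wording above. The abbreviated module already exists on control tablets, but whether it can be opened within ePOCT+ without further work needs checking. An easier exit could slightly raise abandonment. Recording the status and reviewing it at mentorship visits would limit that.
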